14. ADVERSE EVENTS, SERIOUS ADVERSE EVENTS AND REPORTING

14.1 Adverse Events (AEs)

An AE is any untoward medical occurrence in a subject to whom a medicinal product has been administered, including occurrences which are not necessarily caused by or related to that product.

An AE can be:

- Any unfavourable and unintended sign (including reactions from overdose, abuse, incorrect use of any treatment, or interaction)
- Any new disease or exacerbation of an existing disease (e.g. increase in frequency or worsening in nature)
- Any deterioration in measurements of laboratory values or other clinical tests (e.g. vital signs or X-ray) that results in symptoms, a change in treatment, or discontinuation from the IMP
- Recurrence of an intermittent medical condition (e.g. headache) not present at baseline
- Other medical events regardless of their relationship to the IMP, such as accidents, falls and any injuries resulting from them.

AEs will be recorded from the start of the study, i.e. from the first visit to the study unit on Day 1, until the post-study medical visit.

After completion of the 12-week period following the first vaccination (i.e. after Visit 10), AEs will be recorded by the subject in a diary card, and only those deemed to be relevant or significant by the Investigator will be recorded in the eCRF. A relevant or significant AE will be any event that caused the patient to visit any health care professional. These events will be recorded and the Investigator will determine if the event was possibly related to the investigational product. Any event deemed serious will be processed as a SAE in the normal way and if considered related reported as a SUSAR.

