A full medical examination will be performed 12 weeks (Day 85±2 days) following the first study vaccine administration and the following assessments will be carried out: an assessment of the injection site, a pharmacodynamic blood sample will be taken to measure antibody response, physical examination, vital signs, urinalysis, blood samples for haematology and biochemistry, serum pregnancy test and a review of AEs and concomitant medications. This visit signifies the endpoint for the primary endpoint for the study.

Safety Follow-Up (Visit 11)

A safety follow-up visit will be performed 6 months (±2 weeks) following the second study vaccine administration to check the general health, measure vital signs, collect blood for haematology, biochemistry and to assess the immune response of the subject and to review adverse events (AEs).

Subjects do not have to use highly effective contraception following the Day 85 visit, should any subject become pregnant between Day 85 and Day 210, permission will be sought to follow the pregnancy, to obtain data on the outcome of the pregnancy.

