14.3 Recording and Follow up of Adverse Events

Up to Day 85 (Visit 10), the subjects will be instructed to spontaneously report all AEs to the site staff or Investigator as soon as possible. Any AEs observed or reported by a subject and/or staff up to Day 85 (Visit 10) will also be recorded in the eCRF. The Investigator will review results from the physical examinations. All new and aggravated findings, as compared with baseline, must be identified and recorded as AEs in the eCRF. Following Day 85 (Visit 10) AEs will be recorded by the subject in a diary card, and only relevant or significant AEs will be recorded in the eCRF.

AEs already recorded and designated as 'continuing' should be reviewed at each subsequent assessment.

For all AEs, the Investigator must obtain adequate information to determine the outcome of the AE and to assess whether it meets the criteria for classification as an SAE. For all AEs, sufficient information should be obtained by the Investigator to determine the causality of the AE (i.e. study vaccine or other illness). The Investigator is required to assess causality and record that assessment on the eCRF. Follow-up of the AE, after the date of therapy discontinuation, is required if the AE or its sequelae persist. Any AE that is still ongoing at the post-study medical visit will have an outcome of 'ongoing' recorded in the eCRF, however the Investigator will continue to follow up ongoing related AEs and record information in the source documents. Related SAEs will be followed until the event resolves or the event or sequelae stabilise and this information will be reported to the Sponsor using the SAE reporting forms.

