14.4 Serious Adverse Events and Suspected Unexpected Serious Adverse Reactions (SUSARs)

A SAE is any AE that:

- results in death
- is life-threatening
- requires inpatient hospitalization or prolongation of existing hospitalization
- results in persistent or significant disability or incapacity
- consists of a congenital anomaly or birth defect.

Important medical events that may not be immediately life-threatening or result in death or hospitalization but may jeopardise the patient or may require intervention to prevent one of the other outcomes listed in the definition above should also be considered serious.

A SUSAR is an adverse reaction, which is both serious and unexpected.

I4.5 Reporting Timelines

I4.5.1 SAE Reporting

An SAE must be reported immediately (within 24 hours), independent of the circumstances or suspected cause, if it occurs or comes to the attention of the Investigator at any time during the study period. Any SAE with a suspected causal relationship to the IMP occurring at any other time after completion of the study must be promptly reported.

Contact Details for SAE Reporting:

The following mandatory information must be provided to the Sponsor pharmacovigilance contact within 24 hours for each SAE:

- Protocol number
- Subject number
- AE
- IMP
- Investigator's name and contact details

Causality assessment should be completed as soon as possible.

Follow-up information should be actively sought until the SAE has resolved or sequelae have stabilised. Additional information e.g. hospital reports or death certificates, may be requested by the Sponsor and should be anonymised/pseudonymised before transmission and subsequently filed in the Investigator Site File.

The expectedness of an SAE shall be determined by the Sponsor according to the most recent version of the Investigator's Brochure.

I4.5.2 SUSAR Reporting

The Sponsor shall ensure that all relevant information about a suspected unexpected serious adverse reaction (SUSAR), which occurs during the course of a clinical trial in the United Kingdom and is fatal or life-threatening is reported as soon as possible to the MHRA, the competent authorities of any EEA State, other than the United Kingdom, in which the trial is being conducted, and the relevant Ethics Committee. This needs to be done not later than seven days after the sponsor was first aware of the reaction. Any additional relevant information should be sent within eight days of the report.

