The Sponsor shall ensure that a SUSAR which is not fatal or life-threatening is reported as soon as possible and in any event not later than 15 days after the Sponsor is first aware of the reaction.

I4.6 Abnormal Findings from Investigations or Assessments

Abnormal findings from investigations or assessments will be recorded as AEs if the Investigator considers they are clinically significant and/or result in medical intervention. This may include but is not limited to abnormal laboratory results, physical examination findings and vital sign

values/changes.

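### After Visit 10 a new non-serious adverse event reaches the eCRF only if it led to a health-care visit, even if the Investigator would judge it vaccine-related, and the AE status of Visit 11 findings is unclear

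*Combined protocol and SAP*

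**What the plan says.** Up to Visit 10, all AEs observed or reported go into the eCRF (14.3). After Visit 10 the subject keeps a diary card and, under 14.1, "only those deemed to be relevant or significant by the Investigator will be recorded in the eCRF". 14.1 then gives the criterion: "A relevant or significant AE will be any event that caused the patient to visit any health care professional". The next sentence concerns the events that meet it: "These events will be recorded and the Investigator will determine if the event was possibly related to the investigational product". Serious events have their own route: "Any event deemed serious will be processed as a SAE in the normal way and if considered related reported as a SUSAR".

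14.3 repeats the restriction without the definition and without tying it so closely to diary entries: "only relevant or significant AEs will be recorded in the eCRF". The same section requires the Investigator to gather enough information on every AE to determine its cause, and to enter that assessment in the eCRF. No end date is attached to that requirement.

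14.6 deals with test results and examinations: "Abnormal findings from investigations or assessments will be recorded as AEs if the Investigator considers they are clinically significant". It too has no end date, and it does not mention health-care visits. Visit 11 includes vital signs, haematology, biochemistry and an AE review (12.2; Table 1).

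**The concern.** A trial may reasonably collect fewer AEs once its primary window has closed. The difficulty is the basis for the reduction. Whether a woman sees a health care professional says little about whether the vaccine caused the event, and the filter is applied before relatedness is considered. A late related event that is a nuisance but tolerable, and so self-managed, stays on the diary card.

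Visit 11 is called a safety follow-up, and 6.2.2 describes this as the initial study before safety is investigated in pregnant women. The number of late related non-serious events is one of the things the follow-up should supply, and under this rule that number can only be too low or correct.

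The second worry is consistency. If staff can read 14.3 and 14.6 differently, the same Visit 11 abnormality may become a coded AE with a causality entry for one subject and only a listed value for another.

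**Working it through.** The plan gives no figure to reproduce. The check sets the rules side by side for each kind of event that can arise after Visit 10.

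1. **Serious event.** 14.1 processes it as an SAE. 14.5.1 requires reporting "independent of the circumstances or suspected cause, if it occurs or comes to the attention of the Investigator at any time during the study period". It is captured whether or not a health-care visit occurred.
2. **AE that began before Day 85 and continues.** It is already in the eCRF. 14.3 has continuing AEs reviewed at each later assessment and ongoing related AEs followed up. It is captured.
3. **New, non-serious event that led to a health-care visit.** It meets the 14.1 definition, is recorded, and receives a relatedness judgement.
4. **New, non-serious event managed at home.** It fails the 14.1 definition, and neither 14.1 nor 14.3 offers another criterion. It has no eCRF entry, so there is nowhere to enter the causality assessment that 14.3 asks for on all AEs. This holds even if the Investigator, reading the diary, would call it related. It is not recorded.
5. **Clinically significant laboratory or vital-sign finding first seen at Visit 11, with no health-care visit resulting.** 14.6 makes it an AE. 14.1 can be read as filtering diary entries only, in which case 14.6 stands. The sentence in 14.3 is not limited in that way and, read literally, excludes the finding. The text also does not say whether the scheduled Visit 11 itself counts as a health-care visit. The AE status is unclear.

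What remains available in case 5: 15.4.2 includes Visit 11 in the laboratory tests and vital signs. Laboratory values are listed with range position and investigator assessment, vital signs are described in the same terms, and out-of-range emergent values are listed by subject. 15.1.1 lets the Investigator flag a value as abnormal and clinically significant. The data therefore survive; the AE record, MedDRA coding and causality entry may not.

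**Length of the restricted window** (nominal days from Table 1):
- Visit 10 to Visit 11: 210 − 85 = 125 days.
- First dose to Visit 11: 210 − 1 = 209 days.
- Share: 125 / 209 = 0.598, about 60%.

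This is calendar time, not risk. If a share p of new non-serious diary events leads to a health-care visit, the share left unrecorded is 1 − p. The documents give no value of p, nor the number of late events to expect.

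**Effect on the tables.** The TEAE definition in 15.4.2 has a start (first administration) but no end at Day 85. TEAE summaries by relatedness and maximum intensity could therefore pool full collection to Day 85 with filtered collection afterwards.

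**The case against.** The strongest reply is that this is a disclosed, deliberate limit on collection outside the primary window. The primary objective (7.1) ends at Day 85 and collection is unrestricted until then. The filter applies alike to vaccine and placebo, so it does not obviously favour either. Injection sites are examined at every visit from 2 to 10, the last nominally 85 − 29 = 56 days after the second dose, so a persistent local reaction would normally be recorded before the filter starts. 6.3 expects local reactions to be transient. All of this stands. It limits the importance of the point but provides no route for case 4.

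It can also be said that the Investigator deems which events are relevant and could use that discretion, and that 14.3 already asks for causality on all AEs. But 14.1 states what relevant means and names only health-care use. The all-AE requirement in 14.3 shows that the sections need reconciling; it does not put an excluded event into the eCRF.

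Three stronger readings may tempt a reader, and the documents do not support them:
- *Every AE without a health-care visit is lost after Day 85.* Serious events are captured regardless.
- *Clinically significant Visit 11 results are dropped.* They are in the planned safety outputs with the investigator assessment.
- *14.1 flatly contradicts 14.6.* 14.6 concerns findings from investigations and assessments, not symptoms managed at home. For Visit 11 findings, 14.1 can be confined to diary entries so that both sections hold. Only the looser sentence in 14.3 creates the doubt. A significant finding could also itself lead to a health-care visit and so pass the filter.

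**Conclusion.** The point holds for one gap and one ambiguity. The gap: a new, non-serious, self-managed event starting after Day 85 is not recorded in the eCRF even if the Investigator would consider it related, because the filter comes before the relatedness judgement. The ambiguity: 14.3 does not make clear whether 14.6 still governs abnormal findings at Visit 11, and what is at risk there is AE recording, coding and causality, not the values.

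The gap covers a nominal 125 days, about 60% of the time from first dose to Visit 11. The number of events affected cannot be estimated from the documents and may be small. The conclusion assumes that the health-care-visit sentence in 14.1 is the whole definition, since no other criterion is given. The 12-week primary safety assessment is unaffected. This is an inexpensive improvement to late-safety capture, not a threat to the trial's main conclusion.

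**What to change.** - In 14.1 and 14.3, state that after Visit 10 an AE is recorded in the eCRF if it led to a health-care visit, is serious, or is judged at least possibly related when the Investigator reviews the diary at Visit 11.
- State that 14.6 applies to findings at Visit 11, whether or not they led to a health-care visit.
- In 15.4.2 (and the SAP), tabulate TEAEs up to Day 85 separately from those after Day 85, since the collection rules differ and the TEAE definition has no cut-off.

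The diary and the Visit 11 AE review already exist, so no new visit or instrument is needed. The cost is a short wording change, the Investigator's time to judge diary entries, a few extra AE entries and one extra table split.

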14.2 Categorisation of Adverse Events

14.2.1 Intensity Classification

AEs will be classified as mild, moderate or severe according to the following criteria:

- Mild:** Awareness of sign, symptom, or event, but easily tolerated.
- Moderate:** Discomfort enough to cause interference with usual activity and may warrant intervention.
- Severe:** Incapacitating with inability to do usual activities or significantly affects clinical status and warrants intervention.

14.2.2 Causality Classification

The relationship of an AE to the study vaccine will be classified according to the following:

Related: A reaction that: follows a reasonable temporal sequence from administration of the vaccine, follows a known or expected response pattern to the suspected vaccine, could not be reasonably explained by the known characteristics of the subject's clinical state and, if necessary, the reaction returns on re-starting the vaccine (re-challenge).

Unrelated: A reaction that: does not follow a reasonable temporal sequence from administration of the vaccine and for which there is sufficient and conclusive information that the event is not related to the study vaccine.

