6.3 Risk/Benefit Assessment

Antibodies against the full-length Rib, AlphaC, Alp1, Alp2 and Alp3 proteins, from which the GBS-NN and GBS-NN2 are derived to make up the vaccine antigens, naturally occur in women exposed to GBS, and such antibodies are efficiently transferred to the unborn child *in-utero*. Many adults and new-born infants have, therefore, already been naturally exposed to the proteins from which the antigen is derived and to antibodies against these proteins, and no side effects have been attributed as a consequence of such exposure in humans.

[REDACTED]

[REDACTED]. The maximum human dose will be 50 µg, which if administered to a 60 kg woman would equate to 0.83 µg/kg giving a safety margin of at least 60-fold.

The planned excipients in the vaccine formulation are also all well-known from other vaccines, and no novel or non-tested components are used. The proteins in the vaccine are adsorbed with a known adjuvant, Alhydrogel®, (0.5 mg of Al³⁺ per dose), corresponding to the dose used in many other commercial vaccines.

This is a new investigational product; therefore, there are currently no expected AEs related to the product. However, following injection of GBS-NN alone, approximately 30% of the subjects in the study experienced mild pain. Pain post-injection that is worse than mild would be considered to be unexpected. It is not anticipated that adding the two additional antigenic proteins, to GBS-NN, bound to Alum will significantly alter the safety profile. The Investigator is responsible for reporting adverse events (AEs) that occur during the course of the study. Serious adverse reactions that are deemed to be related to the investigational product in the proposed study will be reported as suspected unexpected serious adverse events (SUSAR).

GBS-NN/NN2, like other protein-based vaccines, may theoretically be associated with a transient febrile reaction (body temperature greater than 38.0°C but not greater than 38.7°C) following vaccination. Immune complex-mediated reactions are unlikely given the recombinant nature of GBS-NN/NN2, however, it is still possible that hypersensitivity may occur.

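### Section 14.2.2 requires a known or expected pattern for 'Related', so a well-timed, unexplained reaction of a new kind fits neither causality class

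*Combined protocol and SAP*

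**What the plan says.** Section 14.2.2 defines two classes, with no intermediate class and no default.

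- **Related** lists reasonable timing, an event that "follows a known or expected response pattern to the suspected vaccine", and no reasonable explanation in the subject's clinical state. Return on re-challenge is added, but only if necessary.
- **Unrelated** is an event that "does not follow a reasonable temporal sequence from administration of the vaccine and for which there is sufficient and conclusive information" that it was not caused by the vaccine.

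Other sections bear on how these classes are meant to work:

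- Section 14.3 has the investigator judge the causality of every AE, framed as a choice between the vaccine and another illness.
- Section 14.5.1 treats expectedness as a separate step: "The expectedness of an SAE shall be determined by the Sponsor", against the Investigator's Brochure.
- Section 6.3 says that "there are currently no expected AEs related to the product", and that serious reactions judged related will be handled as SUSARs. For the period after Visit 10, Section 14.1 likewise says "Any event deemed serious will be processed as a SAE in the normal way and if considered related reported as a SUSAR".
- Section 14.1 also says "the Investigator will determine if the event was possibly related to the investigational product", and the fifth trigger in Section 12.7 uses a similar 'possibly related' level. Section 14.2.2 defines no such level.

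**The concern.** The trial's primary objective is safety and tolerability, and Section 6.3 describes the product as new. A reaction of a kind not seen before is one of the things such a study should be able to recognise. Section 14.2.2 makes resemblance to a known or expected pattern a condition for Related, so a well-timed and otherwise unexplained new reaction does not qualify. Nor is it Unrelated, because its timing is plausible.

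The classification has consequences. The one-SAE review in Section 12.7 and the SAE criterion in Section 12.6 both depend on the event being related. Section 15.4.2 summarises TEAEs by relation to the vaccine. An unclassed serious event might fail to set off the first two and could be put in the wrong column of the third.

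**Working it through.** There is no stated figure to reproduce. The check is whether the two definitions cover the case.

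**Inputs, all from Section 14.2.2.** Four yes/no conditions (1 = yes):

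- T: timing is reasonable
- P: pattern is known or expected
- U: not reasonably explained by the subject's clinical state
- C: conclusive information that the event is not related

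Re-challenge is set aside, because the text makes it conditional.

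**Step 1: the definitions as written.** Related = T and P and U. Unrelated = (not T) and C. Four conditions give 2^4 = 16 combinations.

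- Related: T = P = U = 1 with C free, so 2.
- Unrelated: T = 0 and C = 1 with P and U free, so 2 × 2 = 4.
- Both: impossible, because the classes need opposite values of T.
- Neither: 16 − 2 − 4 = 10.

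**Step 2: the case at issue.** A well-timed, new, unexplained reaction with no conclusive information has T = 1, P = 0, U = 1, C = 0. It fails Related on P alone. It fails Unrelated because T = 1. It is in neither class.

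**Step 3: remove the pattern condition.** Related = T and U, with P and C free, gives 2 × 2 = 4. Unrelated stays at 4. Neither falls to 16 − 4 − 4 = 8. The case in Step 2 becomes Related. The 8 that remain are well-timed events explained by clinical state (T = 1, U = 0: 4 combinations) and badly timed events without conclusive information (T = 0, C = 0: 4 combinations).

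These are counts of logical combinations. They are unweighted, some are hardly realistic, and they say nothing about how often such events occur.

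**Step 4: where the class is used.**

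| Rule | Subjects needed | Depends on relatedness? |
|---|---|---|
| 12.7, severe site, severe systemic or persistent febrile reaction | one sentinel, or more than 20% of a cohort (0.20 × 30 = 6, so at least 7 of 30) | yes |
| 12.7, SAE | 1 | yes |
| 12.7, severe non-serious reactions | 2 in the same cohort | yes, at the 'possibly related' level |
| 12.6, SAE | the subject herself | yes |
| 12.6, severe site, severe systemic or persistent febrile reaction | the subject herself | no condition stated |

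One unclassed SAE is enough to miss the single-SAE trigger. The fifth trigger in Section 12.7 cannot replace it, because it covers only non-serious reactions and needs two subjects.

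**The case against.** The strongest reply is that this is a gap in drafting with little practical effect. Much of that stands.

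- **Intent.** The vaccine-or-other-illness framing in Section 14.3 points a well-timed event with no other illness towards the vaccine. Nothing in the documents shows that an investigator would apply Section 14.2.2 literally. Even so, Section 14.2.2 is the stated rule for classification, and it does not carry out that intent.
- **Safeguards.** Under Section 14.5.1 every SAE is reported within 24 hours whatever the suspected cause, and "Follow-up information should be actively sought until the SAE has resolved or sequelae have stabilised". Three of the four criteria in Section 12.6 state no relatedness condition, so a severe systemic or injection-site reaction stops dosing in that subject anyway. The sentinel hold covers serious or unexplained issues, the escalation review in Section 12.5 includes AEs, and Section 15.4.2 lists all TEAEs. These limit the harm but do not supply the missing class or the study-level trigger in Section 12.7.

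A reader might infer that Section 14.2.2 contradicts Sections 6.3 and 14.1, because they treat related serious reactions as unexpected. The documents do not support that. A response pattern and regulatory expectedness are different things. Section 6.3 reports mild pain in about 30% of subjects given GBS-NN alone, yet calls pain worse than mild unexpected. A reaction of a known kind can therefore be Related and still be a SUSAR.

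A reader might also infer that nothing can be Related because no AEs are expected. Section 6.3 itself describes likely local and flu-like reactions, and Section 12.7 presupposes that severe site reactions and fever can be related. The gap concerns reactions that are new in kind.

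**Conclusion.** The point holds in a limited form. On the plain wording of Section 14.2.2, a well-timed, otherwise unexplained reaction of a new kind belongs to neither class. One SAE of this kind might not count as related for the one-SAE review in Section 12.7 or the related-SAE criterion in Section 12.6, and could be misplaced in the TEAE summaries by relatedness. It would not be lost from SAE reporting or from the TEAE listings.

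The size cannot be put as a probability, because the documents give no rate for such events. What can be said is that a single event suffices.

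The conclusion assumes that the listed conditions for Related are joint, which the sentence structure supports, and that the text is applied as written, which the documents do not establish.

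Step 3 might tempt a reader to conclude that every event not shown to be unrelated must be classed as Related. That does not follow. How to treat the remaining unclassed cases, such as delayed unexplained events, is a policy choice for the sponsor and lies outside this point.

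**What to change.** In Section 14.2.2, delete the known-or-expected-pattern condition, or state that a typical pattern supports relatedness but is not required. A well-timed reaction that the subject's clinical state does not reasonably explain is then Related. State that 'possibly related' in Sections 12.7 and 14.1 means this class. Leave expectedness to the sponsor under Section 14.5.1.

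One detail needs care. Read literally, the change also makes Related a well-timed event with an evident outside cause, such as an injury from a fall, if that cause is not thought of as part of the clinical state. A few words saying that the explanation may be such a cause would prevent this.

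The change is to wording only and needs no new data. Causality already recorded would need re-assessment while still blinded. Somewhat more AEs may count as related, so a Section 12.7 review, a Section 12.6 dosing stop or a SUSAR report may occur slightly more often. So may a hold on escalation, because Section 12.5 stops progression to the higher dose if a Section 12.7 criterion is met.
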